- in 7 days if the SAE is unexpected, life-threatening or lethal, and at least possibly related to the investigational product, with a follow-up written report 8 days later
- in 15 days if the SAE is unexpected, but not immediately life-threatening
- in an annual report in all other cases

Follow-Up of All AEs/SAEs: All adverse medical events must be followed until they are resolved, or until all attempts to determine the resolution of the AE/SAE are exhausted. All outcomes and information regarding whether or not the subject was referred to their Primary Care Provider for additional follow-up must be recorded in the source document. Any SAEs and/or unexpected AEs among study participants during the follow-up period will be reported within 24 hours of knowledge of the event to the FDA, to our local IRB and to the Project Officer of this project via fax or phone call. All follow-up AEs will be recorded and followed to resolution only if they are serious, or if the study physician assesses them to be clinically significant.

Periodic Review of the Safety Data: Drs. [name] and [name] will meet prior to the enrollment of the first subject to review the research protocol, informed consent documents and plans for safety and data monitoring of the study. This review will determine the risks and benefits to research subjects, protection and safety of the subjects and offer suggestions for improving the study design. Moreover, Drs. [name] and [name] will meet in a regular basis during the duration of the study. These meetings will take place every 10 weeks for the entire duration of the study. 'Ad hoc' and/or emergency meetings will take place if needed for specific and/or safety reasons. Minutes of these meetings will be taken and filed in the regulatory binder of this project. The goals of these meetings will be to:

- (1) determine adherence to research plan
- (2) review interim analysis, if applicable, and determine specific data to be analyzed

- (3) evaluate end point/stop point rules
- (4) review protocol violations and deviations to assess adequacy of study
- (5) ensure documentation of informed consent
- (6) enrollment (followed eligibility criteria, enrollment numbers, visit compliance, screening failure information)
- (7) discuss investigator or key personnel changes
- (8) review completeness and quality of data collection forms, vital signs, clinical tests, and confidentiality
- (9) evaluate the aggregate analysis of adverse events/serious adverse events

The major outcomes following data review include:

- (1) continuing the trial unchanged
- (2) modifying the protocol and/or consent form
- (3) terminating the study

If the protocol and/or consent form should be changed, or the study should be terminated, [name] will be responsible for all the necessary communications with the Project Officer, the FDA and the Brown University IRB.

Potential Benefits of Proposed Research: There are no benefits of participating in this study. The level of risks and potential side effects are outweighed by the potential for benefits to be gained. However, we believe that the risk-benefit ratio justifies the conduct of this study, given the magnitude of alcohol dependence and the need to identify novel targets for alcoholism.

Importance of the Knowledge to be Gained: Alcohol abuse and dependence is a major public health problem for which treatment options are limited. This study provides an opportunity to explore a novel pathway that could represent a target for possible pharmacological approaches able to help problem drinkers to reduce or stop their alcohol consumption. On this point, this study provides much needed data necessary for potential future clinical trials testing other new possible compounds (glucocorticoid-receptor antagonists).

Inclusion of Women and Minorities

Women will be encouraged to participate in this research. Our experience is that between 29% and 33% of alcoholics in our research centers are women and that about 36% of subjects who enrol in similar studies are women. However, due to the FDA abortifacient indication of mifepristone, women with childbearing potential will be excluded regardless of the birth control methods adopted. Based on [name] alcohol studies, between 15% and 33% of the women enrolled are postmenopausal or surgically sterile; therefore, we expect about 24% of those enrolled in our study to be women. We will attempt to target women for recruitment by advertising in the women's health section of the major state newspaper as well as sections that focus on women's health in local newspapers and magazines. In our radio ads we will target women and women of color who are typically underrepresented in studies of alcoholism.

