Visit#6: Follow-up (one month); END of STUDY.

Study Population: Sixty-five non-treatment-seeking, alcohol-dependent participants will be recruited. Fifty-eight participants will be enrolled for screening with **50 participants (n = 50)** expected to complete the study. Participants will primarily be recruited via advertisements placed in local newspapers and posted on buses.

Safety Measurement/Parameters: Risks of medication side effects will be minimized through careful and detailed screening of participant. Signs of anxiety and stress, adverse events and vital signs will be assessed at each visit by psychometric assessments. Safety laboratory tests will be evaluated at baseline, and at the end of the study participants will receive a behavioral motivational session at the end of Visit 5.

Financial considerations: There will be no cost(s) to participate in this study. The study medications and all procedures that are not part of routine care, but are required for the study, will be provided to the participant. If eligible for the study, participants will receive \$25 for the randomization visit (Visit# 2) and for the follow-up visits (Visits #4 and #6). During the laboratory phase, at each visit (Visits #3 and #5) participants are compensated \$100 + another possible \$3/drink as incentive for not drinking (max \$24). Therefore, each participant may be compensated up to \$323 during the entire study period. Participants will be also compensated for their travel costs.

Specific Aims:

Aim 1: to assess the safety and tolerability of mifepristone and yohimbine while consuming alcohol.

Aim 2: to test the hypothesis that an increase in alcohol craving induced by yohimbine is antagonized by pre-administration with mifepristone.

Aim 3: to test the hypothesis that an initial priming drink and alcohol consumption induced by yohimbine is antagonized by pre-administration with mifepristone.

TABLE OF CONTENTS

PROTOCOL SYNOPSIS	2
TABLE OF CONTENTS	3
SPECIFIC AIMS	4
RATIONALE AND SIGNIFICANCE TO THE ALCOHOL FIELD	5
Stress and alcohol dependence	5
Clinical relevance	5
Pharmacological stress targets	5
Mifepristone	5
Stress-induced models	6
Integration: psychoneuroendocrinology and trauma factors	6
Significance for NIAAA	6
Innovation	6
The Investigator Team	7
The qualified medical personnel during the laboratory sessions	7
RESEARCH DESIGN AND METHODS	8
Overview of Proposed Research	8
Medications and Doses	8
Study Procedures	9
Data Analysis Plan	10

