
PharmD with the double track in Pharmaceutical Science at UCSF, School of Pharmacy (#1 Pharmacy School in the US). She performed research at the prestigious Ernest Gallo Clinical and Research Center in California under the mentorship of [name], now one of the top directors at NIH. This high selective doctoral program allowed her to receive a double concurrent appointment at UCSF in the Neuroscience Department (Gallo Center) and in the Department of Clinical Pharmacology and Experimental Therapeutics (School of Medicine).

[figure not shown]
The study physician, either [name], will be present during the screening visit. They will perform the physical exam and psychological assessments. [name], is a practicing physician and is Board Certified in Addiction Psychiatry. [name] is Staff Psychiatrist at the VA Medical Center at Roger Williams Medical Center and at CAAS; he has extensive alcohol laboratory experience and contributed to the advancement of knowledge in the AUD research field through several selected publications^{23,70-86}. [name] and the RA will immediately call the study physician if any safety issues arise during or between sessions (i.e. CIWA score ≥ 7).

[name] has the support of Research Associates (RA) who have been trained in administering psychological assessments (i.e. CIWA, SCID, HAM-D/A), conducted similar alcohol and pharmacological studies for many years at Brown and included in our peer-review. They also will collect blood, saliva and urine samples and monitor blood pressure and heart rate using a Dinamap Adult Vital Signs Monitor.

METHODS

Overview of Proposed Research. The design will be a randomized within, crossover, double-blind, placebo-controlled human study with mifepristone in non-treatment-seeking alcohol-dependent individuals. The study will be conducted in two consecutive phases with one month washout period (**Figure 1**): Visit #1, Screening; Visit #2: randomization and drug/placebo dispensed; Visit #3: first lab-session: single dose of yohimbine; Visit #4: After one-month washout period (**30 days, plus or minus two days to accommodate the schedule of the next visit**), follow-up and drug/placebo dispensed; Visit #5: second lab-session, single dose of yohimbine, motivational session (MET); Visit #6: follow-up (one month). END of STUDY.

Figure 1 – Study Design

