Visits 3 and 5 (Stress-induction and Alcohol Laboratory Session): All procedures and responsibilities of each member of the research team are described in Appendix Z (page 3 and 5). Participants will be instructed not to consume alcohol for 24 hours and must have a BrAC of 0.00 prior to any assessment. A sample of salivary cortisol will be collected and a single oral dose of 32.4 mg yohimbine will be administered to participants. The lab-session will begin one hour later in order to allow yohimbine to take effect⁹⁶, at which time a second sample of cortisol will be collected. The CR will be run first, followed by the ASA (Assessments Schedule, Appendix Z). The PI will schedule Visit #3 and Visit #5 (alcohol laboratory sessions) only if [name] will be in proximity of CAAS laboratory. The PI will not schedule Visit #3 and Visit #5 if both study physicians are traveling or not in Providence.

Cue-reactivity (CR). The CR will be similar to previously published studies^{73,97-101}. The entire procedure takes about 45 minutes. The water trial provides a controlled baseline that controls for all aspects of stimuli and movement, except for the nature of the beverage. Next, participants will undergo two 3-minute alcohol cue exposure trials that will be identical to the water trial except that the glass of water will be replaced with their preferred alcoholic beverage and the bottle of water will be replaced with the appropriate commercially-labeled alcohol bottle. After every 3-minute beverage exposure, participants will rate their urge to drink alcohol by completing the alcohol urge and craving questionnaire (ACQ) to assess attention to the sight and smell of water and alcohol cues. Saliva (weight in cotton rolls, mg), heart rate (HR; beats/min) and blood pressure (systolic, diastolic, and mean arterial pressure-MAP) will be monitored continuously using a Dinamap Adult Vital Signs Monitor. After the conclusion of the CR, participants will undergo the ASA. Consistent with recommendations¹⁰², participants will be informed they will receive alcohol following the CR. The last of salivary cortisol (by spitting in a tube) will be collected at the end of the CR.

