Visits 4 and 6 (Follow-up): All procedures and responsibilities of each member of the research team are described in Appendix Z (page 4 and 6). After a one-month Washout period (30 days, plus or minus two days to accommodate the schedule of the next visit), participants will be asked to return for a follow-up and for dispensing of medication: mifepristone 600 mg/day or placebo for a week. The purpose of setting a month-long follow-up is because mifepristone may have the potential to "reset" a dysregulated HPA axis. In this manner, we will assess if there is an enduring effect of mifepristone beyond when the drug is stopped. The follow-up after one month will exclude pharmacokinetic mechanisms and will assess if the mifepristone antagonism at GC-receptors is responsible for resetting the HPA axis feedback loop. Due to the distinct circadian rhythm of cortisol, we will schedule Visits 3 and 5 at the same time of day as Visit 1 in order to collect salivary samples to be measured both under natural (Visit 1) and induced-stress response (Visits 3 and 5) conditions. At the follow-up visits, the participants will complete assessments, including a urine drug screening, as outlined in Appendix Z. As there is no medication or alcohol administration during the randomization (Visit #2), medication dispensing (Visit #2 and Visit #4), and follow-ups (Visit #4 and Visit #6), these visits may be conducted without the physical presence of the study physicians in the CAAS laboratory, but preferably within the Providence area.

Compensation: sessions will last approximately 2 hours, and subjects will receive \$25 for participation.

Data analysis

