- A repeated positive urine drug screen at baseline for any illegal substance except marijuana.
- Individuals diagnosed with a current “severe” Substance Use Disorder (SUD) diagnosis, other than alcohol or nicotine
- Meet DSM-5 criteria for a diagnosis of schizophrenia, bipolar disorder, or other psychoses
- An active illness within the past six months of the screening visit that meets the DSM-5 criteria for a diagnosis of Major Depressive Disorder (MDD) or Anxiety Disorder, or history of attempted suicide
- Clinically significant medical abnormalities: unstable hypertension, clinically significant abnormal ECG, bilirubin $>150\%$ of the upper normal limit, ALT/AST $>300\%$ the UNL, creatinine clearance ≤ 60 dl/min
- Current use of psychotropic medications that may have an effect on alcohol consumption
- Current use of any medication involved in the metabolism of alcohol such as aldehyde dehydrogenase (ALDH), alcohol dehydrogenase (ADH) and CYP2E1: Cefamandole, Cefotetan, Sulfamethoxazole, Nitroglycerin, Chlorpropamide, Glyburide.
- Current use of any medication (CYP3A4 inhibitor and substrate) that may interact with mifepristone: cyclosporine, fentanyl, heparin, escitalopram, lovastatin, simvastatin, warfarin
- Current use of any medication (CYP2D6 inhibitor and substrate) that may interact with yohimbine: amitriptyline, doxepin, nortriptyline, venlafaxine
- Medical contraindications for use of mifepristone or yohimbine
- A history of adverse reaction or hypersensitivity to mifepristone or yohimbine
- History of suicide
- History of seizure disorders
- Hypokalemia (low potassium level) <3.5 mEq/L
- Participated in any behavioral and/or pharmacological study within the past **30 days**
- Neuroendocrine disorders
- Taking corticosteroids
- Bleeding disorders
- Pre-existing QT prolongation on ECG
- History of porphyria (Mifepristone progesterone receptor antagonist is an inducer of CYP-450 and therefore may have the ability to precipitate or exacerbate attacks of acute porphyria)
- Not willing to engage in protected sex (condom). **This risk includes both women and men.** Mifepristone long half-life ($t_{1/2} = 18$ hrs) and its three main metabolites retain considerable affinity toward human progesterone and glucocorticoid receptors, with serum level similar to the parent mifepristone and there

are no studies on the presence of mifepristone or metabolites in semen

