Medications and Drug-Drug Interactions: Corcept Therapeutics will provide mifepristone (600 mg, for seven days plus three extra day doses) or matching placebo. Participants will receive a blister pack containing 10 capsules of mifepristone or placebo (7 days + three extra doses). Participants will return for the first follow-up visit and they will receive the additional blister pack. Bayview pharmacy will provide yohimbine (32.4 mg) formulated in a single capsule that will be administered at CAAS under team supervision prior to the alcohol laboratory session. Risks of medication side effects will be minimized through careful and detailed screening of participants *by the PI ([name])* to minimize recruitment of those who might be at higher risk for adverse events, as well as careful and detailed monitoring of adverse events and participant well-being during the study.

Mifepristone: Since mifepristone is a FDA-approved oral medication for the termination of early pregnancy, we will exclude women with childbearing potential regarding the birth control methods used. The following complications or risks have been reported, are known, or may occur with mifepristone: the most commonly reported side effects associated with the use of mifepristone include: abdominal or stomach pain, back pain, diarrhea, dizziness, headache, nausea or vomiting. Other less common side effects associated with the use of mifepristone include: cough, fainting, fever, heartburn, indigestion, lack of strength, or stomach discomfort. Rare side effects associated with the use of mifepristone include: sleepiness, pain during sexual intercourse, pale skin, shaking chills, shortness of breath, stuffy or runny nose, and unusual bleeding or bruising. Mifepristone may cause low blood potassium (hypokalemia); symptoms may include muscle weakness, aches, or cramps, or abnormal palpitations. Subjects with low potassium levels at screening will be excluded. In eligible participants, hypokalemic symptoms will be monitored during the entire study. Mifepristone progesterone receptor antagonist is an inducer of CYP-450 and therefore may have the ability to precipitate or exacerbate attacks of acute porphyria (exclusion criteria).

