Center Alcohol and Addiction Studies

Brown University

TITLE: A Pilot Study on the safety and efficacy of Mifepristone for the prevention of relapses of alcohol drinking

PI: [name]

NCT02243709

IND121984

DATE: December 15 2014

Statistical analysis

Distributional characteristics of outcome measures were examined to evaluate similarity to the normal distribution, detailed descriptive analysis of demographics, substance use, and clinical characteristics were conducted. Comparisons with these characteristics, in relation to enrolled versus completer status, were performed using *t*-tests to analyze continuous variables (e.g., age) and Chi square (χ^2) for categorical variables (e.g., sex, race, smoking status). Attrition rates between the screening visit and follow-up visit were examined descriptively to assess for potential bias. In addition, a logistic regression was performed to test for possible bias due to period (A/B: placebo first, then mifepristone and B/A: mifepristone first, then placebo) or medication carryover (1: placebo and 2: mifepristone), as done in our prior cross-over trial¹.

Primary outcomes: safety and tolerability of oral administration of mifepristone was assessed after 7 days in outpatient setting, and when it was administered with yohimbine and alcohol during the laboratory paradigms. These analyses included comparing the number of adverse events (AEs) between the mifepristone and placebo condition via a χ^2 test. The results were presented using summary statistics such as number of subjects (*n*); mean (*M*); standard deviation (*SEM*) or frequency distributions (%).

Primary outcomes: safety and tolerability assessed by the number of adverse events (AEs) of oral administration of mifepristone was assessed after 7 days in an outpatient setting, and when it was administered with yohimbine and alcohol during the laboratory paradigms. Additional safety and tolerability analysis included hemodynamic response, alcohol pharmacokinetics, and subjective effects of alcohol between the mifepristone and placebo condition (χ^2 test).

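### For the mifepristone dosing weeks the supplied text states only symptom monitoring for low potassium, and the SAP analyses no blood chemistry, so a fall without symptoms would be missed

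*Protocol*

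**What the plan says.** The protocol (Medications and Drug-Drug Interactions, Mifepristone) identifies the risk: "Mifepristone may cause low blood potassium (hypokalemia); symptoms may include muscle weakness, aches, or cramps, or abnormal palpitations". Table 1 makes a measured value an exclusion criterion: "Hypokalemia (low potassium level) <3.5 mEq/L". For the period on study drug, the same Mifepristone paragraph states: "Subjects with low potassium levels at screening will be excluded. In eligible participants, hypokalemic symptoms will be monitored during the entire study".

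The protocol's account of Visits 3 and 5 lists breath alcohol, salivary cortisol, saliva weight, heart rate, blood pressure and questionnaires. Of the start of each session it says: "A sample of salivary cortisol will be collected and a single oral dose of 32.4 mg yohimbine will be administered to participants". It names no blood test there, but it refers the reader to Appendix Z for the full procedures.

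The SAP (Primary outcomes) compares the number of adverse events between conditions and then adds: "Additional safety and tolerability analysis included hemodynamic response, alcohol pharmacokinetics, and subjective effects of alcohol between the mifepristone and placebo condition". No blood chemistry appears in the SAP's safety analyses.

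**The concern.** The protocol relies on a measured potassium value to decide who may enter. Once participants take the drug that is said to lower potassium, the stated check becomes symptoms alone. Symptom monitoring cannot detect a fall that causes none. It is also not specific in this trial: palpitations and muscle weakness are given as signs of low potassium, while the protocol lists an irregular or fast heartbeat among yohimbine's effects and weakness among the signs of adrenal insufficiency.

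Safety and tolerability is the first primary objective in the Synopsis and the primary outcome in the SAP, and the data are meant to support a larger trial. On the stated measures, a finding of no difference in adverse events would say nothing about asymptomatic low potassium. Participants receive yohimbine and alcohol at the point where each dosing week ends.

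**Working it through.** The plan gives no figure for this point, so there is none to reproduce. The check has two parts: what the text provides for, and what a potassium value would add.

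**1. Which visits fall during dosing, and what is stated there**

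| Visit | Position relative to dosing | Blood work named in the text |
|---|---|---|
| 1 | Screening, before any dose | Blood tests; potassium used for exclusion |
| 2 | Randomisation and dispensing | None named; see Appendix Z |
| 3 | Day 7, on drug | None named; see Appendix Z |
| 4 | After the washout of about one month; dispensing | Only a urine drug screen named; see Appendix Z |
| 5 | Day 44, on drug | None named; see Appendix Z |
| 6 | One-month follow-up | Only a urine drug screen named; see Appendix Z |

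Visits 3 and 5 are the only scheduled visits during dosing, one in each condition. They are where a within-person potassium comparison could be made.

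**2. What one value at each of Visits 3 and 5 would give**

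These are illustrations. The rates and SDs are assumed, because the documents give none that can be used. The sample sizes are from the documents: 20, raised to 32 (SAP, Power), and 50 completers (Protocol Synopsis). Participants are taken as independent and attending both sessions.

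- *Upper limit if no case is seen on mifepristone* (one-sided 95%): 1 − 0.05^(1/n) = 13.9% at n=20, 8.9% at n=32, 5.8% at n=50.
- *Chance of at least one case in 32*: 1 − (1 − r)^32 = 47.6%, 80.6% and 96.6% for r = 2%, 5% and 10%.
- *Precision of the within-person difference at N=32*: half-width = t(0.975, 31) × SD/√32 = 2.040 × SD/5.657 = 0.108, 0.144 and 0.180 mEq/L for an SD of the difference of 0.3, 0.4 and 0.5 mEq/L.
- *Yes/no comparison below 3.5 mEq/L, exact McNemar*: with all discordant pairs in one direction, five pairs give p = 2 × 0.5^5 = 0.0625 and six give 2 × 0.5^6 = 0.031, so at least six are needed. With no placebo cases, the chance of six or more in 32 is 9.4% at a 10% rate and 64.0% at 20%.

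The continuous difference is therefore the useful measure. The yes/no count is description only at this sample size.

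**The case against.** The strongest reply is that the gap may lie in the supplied text and not in the trial. The protocol says that Appendix Z contains all procedures for each visit, and the narrative for Visits 3 and 5 does not claim to be complete. A staffing sentence says of the research associates: "They also will collect blood, saliva and urine samples and monitor blood pressure and heart rate using a Dinamap Adult Vital Signs Monitor". It appears to sit under the heading on medical personnel during the laboratory sessions, and it pairs blood collection with the monitor used in those sessions. Another sentence has a phlebotomist drawing blood during the study. Neither names potassium or an on-drug visit, but both leave room for a draw. This stands, and it is why Appendix Z must be checked first. It does not supply the missing analysis: even if potassium was drawn, the SAP does not say that it would be compared.

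The Synopsis also says: "Safety laboratory tests will be evaluated at baseline, and at the end of the study". A reader might infer that the second laboratory test comes at Visit 6, a month after dosing, and so could not help. The documents do not settle this. The sentence is garbled and runs on into the motivational session at the end of Visit 5, which is an on-drug visit, although the study overview places the end of study at Visit 6. I draw no conclusion from the timing of that test.

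There are other safeguards: the screening exclusion, symptom monitoring, physicians alerted to any adverse effect, and short exposure. Symptomatic cases can be recorded as adverse events, as could a low value once measured. These lower the weight of the point. They do not detect a fall that nobody measures and nobody feels.

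**Conclusion.** The point holds as a low-to-moderate, cheap improvement. In the supplied text, potassium is measured for entry, only symptoms are followed on drug, and no blood chemistry enters the SAP safety analyses. On those measures, no upper bound can be put on asymptomatic hypokalaemia during mifepristone. The conclusion rests on the supplied text and could be narrowed to a missing analysis if Appendix Z schedules an on-drug draw that includes potassium.

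Three stronger readings are not supported:

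- *That no blood was taken on drug, or that on-treatment laboratory safety was not assessed at all.* Appendix Z is not available, so an on-drug draw is unstated, not shown to be absent.
- *That about 11 of 32 participants would have undetected low potassium.* This follows from multiplying 32 by the 34% in the protocol's side-effect table. That figure comes with no population, duration or comparator, and need not apply to seven days in screened participants.
- *That the adverse-event comparison is biased.* Nothing here shows that; it is only silent on this one risk.

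**What to change.** First check Appendix Z for a blood draw at Visits 3 and 5. The SAP is written in the past tense, after database lock, so sampling may already be over.

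- **If on-drug potassium was measured:** add to the SAP the within-person mifepristone-minus-placebo difference in mEq/L with its 95% CI, and report n/N below 3.5 mEq/L by condition as description. The cost is one analysis of data already held.
- **If it was not measured and sampling continues:** add serum potassium to any blood already drawn at Visits 3 and 5. Otherwise draw one tube on arrival, at the same time in both sessions, and not between the cortisol samples taken before and after yohimbine. Analyse it as above. Send results to the study physicians, who decide on any action, and not to outcome raters, since a low value could hint at allocation. The cost is at most 32 × 2 = 64 tubes and assays at N=32, drawn by the research assistant who is already a phlebotomist. The downside is one extra venepuncture before a stress challenge, the same in both conditions.
- **If it was not measured and sampling is over:** add one sentence saying that the safety conclusion does not cover asymptomatic hypokalaemia, and claim no more than that.
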